4 INVESTIGATIONAL PLAN

4.1 Study Design and Duration

The study design schematic is presented in Figure 3.1-1.

Figure 4.1-1: Study Design Schematic

The subjects will be treated in both arms until disease progression, unacceptable toxicity, or subject withdrawal of consent.

This study will consist of three phases: screening, treatment, and follow-up. For a complete list of study required procedures, please refer to [Section 5](#).

Screening Phase:

- Begins by establishing the subject's initial eligibility and signing of the informed consent form (ICF).
- Subject is assessed for complete study eligibility within the required timeframe found in Table 7.1-1.
- A pregnancy test for WOCBP should be documented within 24 hours prior to the start of the first dose of study medication.
- All subjects must have at least 2 distinct lesions as documented by a complete physical examination or imaging studies within 4 weeks prior to randomization. Imaging studies must include a CT scan of the involved disease sites and all known sites of resected disease and brain magnetic resonance (MRI) or CT (brain CT allowable if MRI is contraindicated or if there is no known history of resected brain lesions).

Treatment Phase:

- Following confirmation of the subject's eligibility, the randomization call to the Moffitt Cancer Center Biostatistics Core can be made. The subject is randomly assigned to the Arm A (nivolumab + ipilimumab) or Arm B (nivolumab + ipilimumab + SBRT).
- Within 2 weeks from randomization the subject must receive the first dose of study medication (Day 1 of Week 1)
- On-study laboratory assessments should be drawn within 72 hours prior to dosing
- Adverse event assessments for grade ≥ 2 toxicities should be documented at each clinic visit and WOCBP must have a pregnancy test every four weeks +/- 1 week.
- Treated subjects will be evaluated for recurrence every 12 weeks +/- 7 days
- Patient Reported Outcome (PRO) instruments must be completed after randomization, prior to the dose of study therapy.

Follow-up Phase:

- Begins after 1 year of treatment or when the decision is made to discontinue a subject from study therapy.
- Patient may continue on the study drug under the treatment protocol indefinitely during the follow-up phase.
- After completion of the first two follow-up visits, subjects will be followed every 3 months for survival.

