5 STUDY DRUG

This is a non-blinded study which includes investigational products:

Product	Potency	Appearance	Packaging	Storage Conditions
Nivolumab (Solution for Injection)	10 mg/mL	Clear to pale yellow liquid; may contain particles	10 mL/vial	Store at 2-8°C; protect from light or freezing
Ipilimumab (Solution for Injection)	5 mg/mL	Clear to pale yellow liquid; may contain particles	10 mL/vial	Store at 2-8°C; protect from light or freezing

Premedications or medications used to treat infusion-related reactions should be sourced by the local site. Solutions used as diluents (0.9% Sodium Chloride or 5% Dextrose) should also be sourced by the local site.

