Review of concomitant medications	x	x	x	x	x	x	
Pregnancy Test	x			x		x	Every 4 weeks \pm 1 week. Serum or Urine.
Laboratory Tests	x		x	x	x	x	Within 72 hrs prior to dosing/SBRT to include CBC w/differential, LFT's, BUN or serum urea level, creatinine, Ca, Mg, Na, K, Cl, LDH, Glucose, amylase, lipase, TSH (with reflexive Free T4/T3)
Exploratory Biomarker Assessments							
Plasma	x	x	x		x		Prior to dosing/SBRT
Peripheral Blood Mononuclear Cells (PBMCs)	x	x	x		x		Prior to dosing/SBRT
Efficacy Assessments							
Surveillance Assessments	Every 12 weeks (\pm 7 days) from first dose of study treatment through 12 months (until distant recurrence)						Clinical exam and/or CT scan of the involved disease sites and all known sites of resected disease and brain MRI (brain CT allowable if MRI is contraindicated or if there is no known history of resected brain lesions). Use same imaging method as was used at screening/baseline.
Study Drug							
Randomize	x						
Study Treatment	x	RT	x	x	x	x	First dose to be administered within 14 days of randomization. See Section 5.5.
Outcome Research							
EORTC-QLQ-C30	x				x		Prior to dosing. D1W1 should be completed after randomization but prior to dosing.
EQ5D (optional)	x				x		
WPAI:GH (optional)	x				x		
Health Care Resource Utilization (optional)	x				x		

Table 7.1-3: On-Treatment Assessments Week 11 - Week 21

Procedure	Wk11	Wk13	Wk15	Wk17	Wk19	Wk21	Notes
Safety Assessments							
Targeted Physical Examination	x	x	x	x	x	x	
Vital Signs	x	x	x	x	x	x	Including BP, HR, temperature
Oxygen saturation	x	x	x	x	x	x	By pulse oximetry prior to dosing
Weight and performance status	x	x	x	x	x	x	Within 72 hours of dosing
Adverse Events Assessment	Continuously						See Section 6.8. and Section 8
Review of concomitant medications	x	x	x	x	x	x	
Laboratory Tests	x	x	x	x	x	x	Within 72 hrs prior to dosing to include CBC w/differential, LFT's, BUN or serum urea level, creatinine, Ca, Mg, Na, K, Cl, LDH, Glucose, amylase, lipase, TSH (with reflexive Free T4 and T3)
Pregnancy Test		x		x		x	Every 4 weeks ± 1 week. Serum or Urine.
Exploratory Biomarker							
Plasma		x					Prior to dosing
Peripheral Blood Mononuclear Cells (PBMCs)		x					Prior to dosing
Efficacy Assessments							

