Work Productivity and Activity Impairment: General Health (WPAI:GH) is a 6-item questionnaire yielding four different types of scores. The WPAI:GH was created as a patient-reported quantitative assessment of the amount of absenteeism (work time missed), presenteeism (impairment at work), work productivity (overall work impairment/absenteeism plus presenteeism) and daily activity impairment attributable to general health. WPAI:GH outcomes are expressed as impairment percentages, with higher numbers indicating greater impairment and less productivity, ie, worse outcomes. The recall period in all WPAI:GH validation studies is 7 days. The general literature on recall burden suggests that a longer recall period would not be suitable for the type of information being elicited in the WPAI:GH. In theory, a shorter recall period would improve accuracy of WPAI:GH responses, but this has not been tested. Assessment of work productivity will be conducted at each site (or remotely) with the appropriately translated and validated version of the WPAI:GH. All PRO instruments will be administered during on-study, and follow-up phases as outlined in Tables of Section 5.1, respectively, to all randomized subjects. Healthcare resource utilization data (eg, hospitalizations, non-protocol specified medical visits, diagnostics, etc) will be collected for all randomized subjects. The resource utilization capture is specific to hospital admission utilization data and non-protocol specified visits related to study therapy. Resource utilization questions will be asked as outlined in Table of Section 5.1 during screening, on-study, and follow-up phases, respectively.

An **Adverse Event (AE)** is defined as any new untoward medical occurrence or worsening of a preexisting medical condition in a clinical investigation subject administered study drug and that does not necessarily have a causal relationship with this treatment. An AE can therefore be any unfavorable and unintended sign (such as an abnormal laboratory finding), symptom, or disease temporally associated with the use of study drug, whether or not considered related to the study drug.

The causal relationship to study drug is determined by a physician and should be used to assess all adverse events (AE). The causal relationship can be one of the following:

Related: There is a reasonable causal relationship between study drug administration and the AE.

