9.2.2 Secondary Endpoint(s)

The first secondary endpoint is PFS. PFS will be programmatically determined based on the disease progression date provided by the investigator and is defined as the time between the date of randomization and the date of first progression (local, regional or distant metastasis) or death (whatever the cause), whichever occurs first. (Note: a subject who dies without reported progression will be considered to have progressed on the date of death.) For subjects who remain alive and whose disease has not progressed, PFS will be censored on the date of last evaluable disease assessment.

The second secondary endpoint (OS) is defined as the time between the date of randomization and the date of death. For subjects without documentation of death, OS will be censored on the last

date the subject was known to be alive. OS will be followed continuously while subjects are on the study drug and every 3 months via in-person or phone contact after subjects discontinue the study drug.

To third secondary endpoint to compare the local control of irradiated tumor provided by SBRT in combination with nivolumab versus nivolumab and ipilimumab will be assessed by the local control rate of the irradiated lesion.

The fourth secondary endpoint (to assess the safety and tolerability of nivolumab, SBRT and ipilimumab) will be measured by the incidence of adverse events, serious adverse events, deaths, and laboratory abnormalities.

The fifth secondary endpoint (to evaluate PD-L1 expression as a predictive biomarker) will be measured by the endpoint RFS based on PD-L1 expression level.

The sixth secondary objective (to evaluate HRQoL) will be measured by mean changes from baseline in the EORTC-QLQ-C30 global health status/QoL composite scale and by mean changes from baseline in the remaining EORTC QLQ-C30 scales in all randomized subjects.

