9.3.4 Outcomes Research Analyses

EORTC QLQ C-30

The analysis of EORTC QLQ C-30 will be performed in all randomized who have an assessment at baseline and at least one follow-up assessment.

All scales and single items are scored on a categorical scales and linearly transformed to 0-to-100 scales with higher scores for a functional scale representing higher levels of functioning, higher scores for the global health status/quality of life representing higher levels of global health status/quality of life and higher scores for a symptom scale representing higher level of symptoms.

EORTC QLQ C-30 global health status/QoL composite scale data and the remaining EORTC QLQ C-30 scale data will be summarized by timepoint using descriptive statistics for each treatment arm. Exploratory analyses may be performed to examine differences between the 2 arms.

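### Baseline quality-of-life forms are completed after randomization in a non-blinded trial, so by-arm change scores can carry a reaction to the allocation

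*Combined protocol and SAP*

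**What the plan says.** Section 4.1, under the treatment phase, fixes the timing: "Patient Reported Outcome (PRO) instruments must be completed after randomization, prior to the dose of study therapy". The note to the QLQ-C30 row of Table 7.1-2 says the same: "D1W1 should be completed after randomization but prior to dosing". The optional EQ-5D and WPAI:GH are also first scheduled at Week 1.

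No earlier questionnaire exists. Table 7.1-1 (screening) has no patient-reported outcome row, and Section 7.6 places the instruments after screening: "All PRO instruments will be administered during on-study, and follow-up phases as outlined in Tables of Section 5.1, respectively, to all randomized subjects".

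Section 5 opens: "This is a non-blinded study which includes investigational products". Section 4.1 allows up to 2 weeks between randomization and the first dose. No section says when the patient learns the arm, or asks sites to withhold it until the form is done.

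Section 9.2.2 says the quality-of-life objective "will be measured by mean changes from baseline in the EORTC-QLQ-C30 global health status/QoL composite scale", and likewise by change on the remaining scales. Section 9.3.4 restricts the analysis to randomized subjects "who have an assessment at baseline and at least one follow-up assessment". It plans descriptive summaries by arm and timepoint; differences between the arms may be examined in exploratory analyses. Baseline is not defined separately, but the Week 1 form is the only one before dosing.

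**The concern.** In an open trial, a baseline taken after allocation can itself respond to allocation. Both arms receive the same drugs, so the news that differs between patients is whether they will receive SBRT. Relief or disappointment could reach the form: Appendix 5 asks about tension, worry, irritability, depression, overall health and overall quality of life. Items 6 to 30 carry a one-week recall. If the gap between randomization and the form is 7 days or more, that week can lie wholly after the patient knows the arm.

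One form is the reference for all QLQ-C30 changes, so an arm-specific shift in it would enter the change on every affected scale. At stake is the reading of a named secondary objective. Section 1.4.10 says the instrument is there to assess changes from baseline in the different arms.

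**Working it through.** The plan gives no quality-of-life effect size, standard deviation or power, so there is no figure to reproduce. The calculation below only shows what an assumed shift would do.

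**Inputs from the documents.** Up to 2 weeks from randomization to first dose (Section 4.1). Screening from Day -28 (Table 7.1-1). About 50 subjects randomized 1:1, so about 25 per arm (Synopsis); 24 per arm in Section 9.1.1. Tests two-sided at 0.05 (Synopsis). These arm sizes are upper limits for the questionnaire analysis, which also needs a baseline and a follow-up form.

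**Assumed inputs.** A baseline shift d in one arm only, 0.1 to 0.5 SD; correlation rho between baseline and follow-up, 0.3 to 0.7; equal SDs at both times; no true difference at follow-up; the reaction gone by the follow-up visit.

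**Step 1: how the shift passes through.** Let r0 be the arm difference in reaction at baseline and rt the difference at a later visit. The bias in the between-arm difference in change is rt - r0. If the reaction has gone (rt = 0), the bias is -r0: one-for-one with opposite sign. If it persists in full (rt = r0), it cancels.

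**Step 2: formulas, in SD units, n per arm.**
- Change score: absolute bias d; SE = sqrt(2(1 - rho)) x sqrt(2/n).
- Baseline-adjusted: absolute bias rho x d; SE = sqrt(1 - rho^2) x sqrt(2/n).
- Follow-up score alone: bias 0; SE = sqrt(2/n).
- False-positive rate = Phi(-1.96 + bias/SE) + Phi(-1.96 - bias/SE).

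**Step 3: n = 25, rho = 0.5.** sqrt(2/25) = 0.283. The SE is 1 x 0.283 = 0.283 for change and 0.866 x 0.283 = 0.245 after adjustment. At d = 0.2, the change-score bias is 0.2/0.283 = 0.71 SE and the adjusted bias is 0.10/0.245 = 0.41 SE.

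| Assumed shift d (SD) | Change score: false-positive rate | Adjusted: bias (SD) | Adjusted: false-positive rate |
|---|---|---|---|
| 0.1 | 6.4% | 0.05 | 5.5% |
| 0.2 | 10.9% | 0.10 | 6.9% |
| 0.3 | 18.6% | 0.15 | 9.4% |
| 0.5 | 42.4% | 0.25 | 17.5% |

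For rho from 0.3 to 0.7 at d = 0.2, the rate is 9.2% to 15.0% for change and 5.6% to 10.7% after adjustment. For the follow-up score alone it stays at 5%.

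**Step 4: the same on the 0-100 scale, n = 24.** Assume a 5-point one-arm shift and an SD of change of 15, 20 or 25. SE = SD x sqrt(2/24) = 4.33, 5.77 or 7.22 points, so the bias is 5/SE = 1.15, 0.87 or 0.69 SE.

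**Step 5: after the fix.** With the form completed before allocation, r0 is zero by design, and so is the bias from this source.

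**The case against.** The strongest reply is that little in the plan depends on this. Section 9.3.4 commits only to descriptive summaries, and the between-arm look is optional and exploratory. Section 1.3.2 speaks of evaluating quality of life, where it speaks of comparing PFS and OS. This stands and limits the weight of the point. It does not remove it, because changes shown side by side by arm carry the same distortion without a test.

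A reader might infer that every quality-of-life comparison is biased beyond repair. The documents do not support that. The by-timepoint summaries of Section 9.3.4 allow follow-up scores to be compared between randomized arms without the baseline, and adjustment shrinks the bias to rho x d. What is lost is an unaffected change score.

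A reader might also count SBRT planning as something only Arm B meets after allocation. Section 6 says planning should begin at registration, before randomization, so the text does not make it an Arm B exposure.

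The 2-week window is a maximum. Table 7.1-2 lists randomization in Week 1, beside the questionnaire, although Table 7.1-1 lists it at screening. If both fall on one day, the recall week lies mainly before allocation; the patient may still know the arm while answering.

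Finally, the shift is assumed, and the table needs it to have faded by follow-up. That is correct: a persisting reaction cancels partly or wholly in the change score.

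**Conclusion.** The point holds as a design weakness that is cheap to correct. The plan requires a post-randomization baseline in a non-blinded trial, has no earlier form to fall back on, and defines the endpoint as change from that baseline. An arm-specific reaction present at baseline but not later would distort the by-arm changes and any exploratory comparison of change.

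Whether such a reaction occurs, how large it is and in which direction are unknown. The working is conditional on an assumed one-arm shift, an assumed correlation and a reaction that fades; it is not evidence that bias has occurred. The objective response rate, the two-stage sample size, the selection between arms and the safety analysis do not use this form and are unaffected.

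**What to change.** In Section 4.1 and Tables 7.1-1 and 7.1-2, require the baseline QLQ-C30, and the optional EQ-5D and WPAI:GH where used, after consent and before the randomization call, as close to randomization as practical. At the least, require completion before the allocation is disclosed to the patient. A Week 1 pre-dose form may stay as a second record, stated not to be the baseline. Section 9.3.4 should name the form that counts as baseline.

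For patients already enrolled under the current rule, report baseline scores by arm and the interval from randomization to the form, and state the limitation. Any exploratory between-arm look at these patients can include follow-up scores alone.

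The cost is small. It is the same questionnaire, moved earlier. The baseline lies further from the first dose: up to 14 days if completed at randomization, and up to 28 + 14 = 42 days, about 6 weeks, if completed at the start of screening. A long gap could mix pre-treatment decline into the within-arm changes, hence the request to stay close to randomization. A mid-trial change leaves two baseline definitions, to be reported separately. The change does not stop knowledge of the arm from influencing later forms, which is a feature of any open trial.

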4.2 Concomitant Treatments

4.2.1 Prohibited and/or Restricted Treatments

- The following medications are prohibited during the treatment and follow-up phases (before recurrence) of the study (unless utilized to treat a drug-related adverse event):
- Immunosuppressive agents

- Immunosuppressive doses of systemic corticosteroids (except as stated in Section 4.4.2)
- Any concurrent anti-neoplastic therapy (including, but not limited to chemotherapy, hormonal therapy, immunotherapy, radiation therapy, or standard or investigational agents for treatment of Merkel cell carcinoma other than specified per protocol).

4.2.2 Permitted Therapy

Subjects are permitted the use of topical, ocular, intra-articular, intranasal and inhalational corticosteroids (with minimal systemic absorption). Physiologic replacement doses of systemic corticosteroids are permitted even if > 10 mg daily prednisone (or equivalent). A brief course of corticosteroids for prophylaxis (eg, for contrast dye allergy) or for treatment of non-autoimmune conditions (eg, delayed-type hypersensitivity reaction caused by a contact allergen) is permitted.

Intravitreal injections of vascular endothelial growth (VEGF) inhibitors are permitted if used according to the approved ocular indication, such as macular degeneration.

4.3 Discontinuation of Subjects following any Treatment with Study Drug

Subjects MUST discontinue investigational product (and non-investigational product at the discretion of the investigator) for any of the following reasons:

- Subject's request to stop study treatment
- Progression of the target lesion
- Any clinical adverse event (AE), laboratory abnormality or intercurrent illness which, in the opinion of the investigator, indicates that continued participation in the study is not in the best interest of the subject
- Termination of the study by Bristol-Myers Squibb (BMS)
- Loss of ability to freely provide consent through imprisonment or involuntarily incarceration for treatment of either a psychiatric or physical (eg, infectious disease) illness
- Additional protocol specified reasons for discontinuation (see Section 4.5.7).

In the case of pregnancy, the study drug will be permanently discontinued in an appropriate manner unless the investigator determines a possible favorable benefit/risk ratio that warrants continuation of study drug.

All subjects who discontinue study drug should comply with protocol specified follow-up procedures as outlined in [Section 7](#). The only exception to this requirement is when a subject withdraws consent for all study procedures including post-treatment study follow-up or loses the ability to consent freely (ie, is imprisoned or involuntarily incarcerated for the treatment of either a psychiatric or physical illness).

If study drug is discontinued prior to the subject's completion of the study, the reason for the discontinuation must be documented in the subject's medical records and entered on the appropriate case report form (CRF) page.

4.4 Post Study Drug Study Follow up

In this study, ORR, PFS, OS and toxicity are key endpoints. Post study follow-up is of critical importance and is essential to preserving subject safety and the integrity of the study. Subjects who

discontinue study drug must continue to be followed for collection of outcome and/or survival follow-up data as required and in line with Section 7 until death or the conclusion of the study.

4.4.1 *Withdrawal of Consent*

Subjects who request to discontinue study drug will remain in the study and must continue to be followed for protocol specified follow-up procedures. The only exception to this is when a subject specifically withdraws consent for any further contact with him/her or persons previously authorized by subject to provide this information. Subjects should notify the investigator of the decision to withdraw consent from future follow-up in writing, whenever possible. The withdrawal of consent should be explained in detail in the medical records by the investigator, as to whether the withdrawal is from further treatment with study drug only or also from study procedures and/or post treatment study follow-up, and entered on the appropriate CRF page. In the event that vital status (whether the subject is alive or dead) is being measured, publicly available information should be used to determine vital status only as appropriately directed in accordance with local law.

4.4.2 *Lost to Follow-Up*

All reasonable efforts must be made to locate subjects to determine and report their ongoing status. This includes follow-up with persons authorized by the subject as noted above. Lost to follow-up is defined by the inability to reach the subject after a minimum of three documented phone calls, faxes, or emails as well as lack of response by subject to one registered mail letter. All attempts should be documented in the subject's medical records. If it is determined that the subject has died, the site will use permissible local methods to obtain the date and cause of death.

If investigator's use of third-party representative to assist in the follow-up portion of the study has been included in the subject's informed consent, then the investigator may use a Sponsor- retained third-party representative to assist site staff with obtaining subject's contact information or other public vital status data necessary to complete the follow-up portion of the study. The site staff and representative will consult publicly available sources, such as public health registries and databases, in order to obtain updated contact information. If after all attempts, the subject remains lost to follow-up, then the last known alive date as determined by the investigator should be reported and documented in the subject's medical records.

